5.1. Study objectives

The EPSILON study aims to comparatively evaluate the submucosal injection using ORISE™ gel and glycerol during an ESD procedure in a specific population with superficial gastric and rectal (pre)neoplastic lesions.

5.2. Study endpoints

5.2.1. Primary

- Increase the dissection speed of the ESD procedure (defined as the dissected surface (mm²)/ESD duration (min)). The dissected surface is defined as maximal diameter of specimen (mm) x perpendicular minimal diameter of specimen (mm) measured on ex-vivo pinned stretched specimen onto a cork. ESD duration is defined as the time from first submucosal injection to final cut time.

5.2.2. Secondary

- Total procedure duration (from scope insertion to scope retrieval) (min)
- Number of per-procedural bleeding (+ severity scale: oozing / severe non pulsating/ severe pulsating)
- Total hemostatic time (addition of each hemostasis time for each per-procedural bleeding)

EndoscoPic Submucosal Dissection using gel versus glycerol for submucosal injection: a randomized controlled multicentric trial (EPSILON)

Version 1 – dated 21/07/2021

- Need for haemostatic forceps during ESD
- Difficulty of the dissection (scale)
- Amount of submucosal solution (glycerol or gel) used for ESD in ml
- Combined use of saline through the knife during ESD (number and ml)
- Number of needle injection dots during ESD (initially / during ESD)
- Need to adjust electrosurgical settings during ESD
- Clear visualisation of the plane of dissection during ESD (scale). The scale will be defined according the endoscopists evaluation of the delineation between the submucosa ad the underlying muscular layer:
 - Very-good visualization: clear delineation between the two layers with clear visualization of the blood vessels.
 - Good visualization: mostly clear delineation between the two layers, but with blurred regions
 - Bad visualization: delineation between the two layers is unclear (i.e.: fibrosis)
- Rate of en-bloc dissection (defined as endoscopic resection of the targeted area in one bloc)
- Rate of complete endoscopic resection (defined as endoscopic evaluation of complete removal of the targeted area in the treated organ)
- Quality assessment of the pathological specimen (absolute measure of the depth of resected submucosa on the specimen, rate of clear (horizontal and vertical) margins)
- Adverse events:
 - Per-procedural (incidence of all adverse technical events during the procedure)
 - Early (clinical and laboratory at 24 h post procedure according to CTCAE v 5.0)
 - Late (clinical at 2-3 weeks follow-up)

6. Study design

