6.6. Screening period (Day -15 to day -1)

The following screening procedures will be performed for all potential patients at the screening conducted during the screening period and prior to randomization:

- If possible, High-definition gastroscopy/rectoscopy for lesion evaluation (using chromoendoscopy and near-focus)
- Signature of informed consent witnessed by the Investigator or designated person.
- Patient randomization number allocation.
- Check medical history/demographics.
- Check inclusion/exclusion criteria
- Physical examination
- Check concomitant/prior medication (within 1 month prior to Screening)

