6.7. Treatment period (Day 0-1)

- Procedure (Day 0): photo documentation of the lesion, ESD procedure, photo documentation of the specimen and resection field.
- Day 0 to +1 : clinical and biological follow-up and discharge (i.e. if no adverse effect is observed). Duration of hospital stay for subjects post procedure is determined by local healthcare practice and healthcare system guidelines and is left at the investigator's discretion.

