According to randomization, using a 25G needle, the lesion will be lifted with a Glyceol solution with indigo blue dye or ORISE™ gel. Mucosal incision will be performed using Dry Cut mode, (E3 30 watts Erbe VIO 300D, E 3.5 Erbe VIO 3; Tubingen, Germany) and subsequent submucosal dissection using dry cut or swift coagulation mode, (VIO 300 E4 30watts; VIO3 E3.5). After mucosal opening, further lifting during the ESD will be performed using the needle or the tip of the knife pushed into the submucosal space with the Glyceol or ORISE™ gel according to randomization. Added saline injected through the tip of the knife is allowed in both groups (with recorded volume) according to the endoscopists convenience. Visible vessels and bleedings will be coagulated with the knife tip (slowly using swift coag E4 30W or using Forced coag E1 15W) or a 4mm (rectum) or 5mm (stomach) coagulation forceps (Coagrasper, Olympus), using soft coagulation (VIO 300 Effect 5, 50 watts (rectum) / 80 watts (stomach); VIO3 E 5.5). For gastric ESD, 80mg of Intravenous PPI will be given during the procedure and 12h later; at discharge PPI 40mg BID will be given after gastric ESD. After the resection, the specimen will be pinned on a cork (or equivalent) to stretch it moderately and expose the lateral margins. Then, measures of the maximal diameter (mm) and perpendicular minimal diameter will be obtained and recorded by picture capture using the scope. Thereafter, it will be immersed into formaldehyde and sent to the pathologic lab.

Patients will remain hospitalized overnight and a blood test will be performed before their discharge.

9. Assessments per procedure

- Duration of ESD procedure defined as the time of first injection to final cut time
- Total duration of the endoscopic procedure (from endoscope insertion to scope retrieval)
- Calculated speed of the dissection (surface dissected (mm²)/ESD duration (min)).
- Number of per-procedural bleeding (+ severity scale: oozing / severe non pulsating/ severe pulsating)
- Total hemostatic time (addition of each hemostasis time for each per-procedural bleeding)
- Need for haemostatic forceps during ESD
- Difficulty of the dissection (scale)
- Amount of submucosal solution (glycerol or gel) used for ESD in ml

EndoscoPic Submucosal Dissection using gel versus glycerol for submucosal injection: a randomized controlled multicentric trial (EPSILON)

Version 1 – dated 21/07/2021

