10.2. Definition and assessment of (serious) adverse events and other safety related events

10.2.1. Adverse Event (AE)

Any untoward medical occurrence, unintended disease or injury or any untoward clinical signs (including an abnormal laboratory finding) in subjects, users or other persons whether or not related to the investigational medical device.

NOTE 1: This definition includes events related to the investigational device or the comparator. NOTE 2: This definition includes events related to the procedures involved.

NOTE 3: For users or other persons, this definition is restricted to events related to investigational medical device.

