4.2 Baseline Data

Subject demographics and clinical history will be summarized using descriptive statistics (e.g., mean, standard deviation, n, minimum, maximum) for continuous variables and frequency statistics for discrete variables.

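### Early adverse events include laboratory findings, but no pre-ESD laboratory value is recorded and no new-or-worsened rule exists, so abnormalities that predate ESD may be counted in both arms

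*Protocol*

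**What the plan says.** Protocol 5.2.2 divides adverse events into per-procedural, early and late. The early class reads "Early (clinical and laboratory at 24 h post procedure according to CTCAE v 5.0"; SAP 4.1 repeats it.

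The laboratory information comes from one sample. Protocol 8.2 states: "Patients will remain hospitalized overnight and a blood test will be performed before their discharge". Protocol 6.7 describes Day 0 to +1 as "clinical and biological follow-up and discharge (i.e. if no adverse effect is observed". The analytes are not named.

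Before the procedure, Protocol 6.6 opens its list with "The following screening procedures will be performed for all potential patients at the screening conducted during the screening period and prior to randomization". The items are endoscopy if possible, consent, a randomization number, history and demographics, eligibility, physical examination and medication. No blood test is among them. Protocol 8.1 mentions only imaging as further work-up. SAP 4.2 limits baseline data to this: "Subject demographics and clinical history will be summarized using descriptive statistics".

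Protocol 10.2.1 includes in its definition of an adverse event "any untoward clinical signs (including an abnormal laboratory finding) in subjects", whether or not the event is related to the device. Neither document contains a treatment-emergent, new-or-worsened or change-from-baseline rule.

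**The concern.** A patient with a gastric or rectal neoplasm may come to ESD with a laboratory value already out of range, from the lesion or from another illness. Under this plan, the first value the trial records is the one taken after ESD. Nothing in the trial data would then separate an abnormality that was already there from one that arose with the procedure.

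What is at stake is the laboratory part of one secondary safety endpoint. Counting pre-existing abnormalities would overstate the early event rate of both solutions and pull the two arms closer together. A missing pre-ESD value cannot be reconstructed from the trial's own data after the event, so the rule has to be set before enrolment.

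**Working it through.** **1. The plan's own figure.** The only computed number is the sample size for dissection speed (Protocol 6.2, SAP 3.1.1). Inputs: means 17.11 and 22.24, SDs 18.27 and 10.26, two-sided alpha 0.05, power 80%, 1:1 allocation. At 133 per arm, SE = √((18.27² + 10.26²)/133) = √(439.06/133) = 1.817, and 5.13/1.817 = 2.82. The Welch test (noncentral t) has power 0.802 at 133 per arm and 0.799 at 132. The stated 133 reproduces and does not depend on the present point. The plan gives no figure for early adverse events.

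**2. Can the plan separate old from new?** Set side by side:

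- *After ESD:* one blood test (Protocol 8.2), graded by CTCAE (5.2.2).
- *Before ESD:* no laboratory value in Protocol 6.6, Protocol 8.1 or SAP 4.2. Table 1 has no laboratory row either, but it also omits the discharge blood test that 8.2 requires, so its silence proves little.
- *Collection window:* Protocol 10.1 collects events from consent. An abnormality known to be older falls outside the window, but without an earlier value this cannot be checked.
- *Relatedness:* Protocol 10.3 has underlying and concurrent illness considered. The endpoint, however, is not restricted to related events. The scale in 10.3, set out for serious events, places cases that cannot be assessed under possible.
- *Dating:* SAP 5.1 assigns an event with no onset date to the day of the procedure.

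Some known conditions would be recognised. An unmeasured or mild abnormality would not be.

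**3. Size, on assumed rates.** Let p be the true new-onset rate. Let b be the share of patients whose pre-existing abnormality is counted despite the safeguards. Assume b is the same in both arms and independent of new events. Then:

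- observed rate = b + (1 − b)p
- observed difference = (1 − b) × true difference

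Example, b = 0.20 and p = 0.10 (glycerol) versus 0.05 (gel): 0.20 + 0.80 × 0.10 = 0.28; 0.20 + 0.80 × 0.05 = 0.24; difference 0.04; ratio 0.28/0.24 = 1.17.

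| b | True 10% vs 5%: observed | Difference (points) | Ratio | True 20% vs 10%: observed | Difference (points) | Ratio |
|---|---|---|---|---|---|---|
| 0% | 10.0 vs 5.0 | 5.0 | 2.00 | 20 vs 10 | 10.0 | 2.00 |
| 10% | 19.0 vs 14.5 | 4.5 | 1.31 | 28 vs 19 | 9.0 | 1.47 |
| 20% | 28.0 vs 24.0 | 4.0 | 1.17 | 36 vs 28 | 8.0 | 1.29 |
| 30% | 37.0 vs 33.5 | 3.5 | 1.10 | 44 vs 37 | 7.0 | 1.19 |
| 40% | 46.0 vs 43.0 | 3.0 | 1.07 | 52 vs 46 | 6.0 | 1.13 |

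At b = 20%, 0.20 × 133 = 26.6, or about 27 patients per arm, would carry an event that predates ESD. If the true prevalence were 20% but history and causality review removed half, the 10% row would apply (0.20 × 0.5 = 0.10). The difference is eroded much less than the ratio.

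**The case against.** The strongest reply is that the definition in Protocol 10.2.1 does not make every out-of-range value an adverse event. A reader might infer that it does. The text gives a laboratory finding as an example of an untoward sign, which leaves room for judgement. With collection starting at consent, and with history, examination, medication and causality review in place, an investigator can set aside a known anaemia. This stands, and it is why the point is that such abnormalities may be counted, not that they will be. It does not remove the gap: the judgement has no recorded value to rest on, follows no written rule across four centres, and is made in an open-label trial.

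A reader might also infer that the trial's bleeding hypothesis depends on this blood test. It does not. Bleeding is measured directly by number and severity, haemostatic time and use of forceps, and the documents do not say that haemoglobin is among the analytes.

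Nor is it a defect that a fall within the normal range goes unseen, because the endpoint is CTCAE-graded events, not laboratory change.

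Finally, sites may already draw routine bloods before anaesthesia. If so, an investigator could consult them, but the documents neither require nor record them. That makes the remedy cheap; it does not make it unnecessary.

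**Conclusion.** The point holds as a gap in recording and in the counting rule. As written, the plan cannot separate laboratory abnormalities that predate ESD from new ones, so some may enter the early-event count in both arms. They would be counted in the endpoint, which is not the same as being judged caused by ESD.

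The size cannot be derived from the documents, which give neither an early-event rate nor a prevalence of pre-existing abnormality. All figures in the table rest on assumed values.

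A reader might infer a bias towards one solution. The documents do not support that: randomization makes pre-existing abnormality similar in the two arms in expectation, so the effect is inflation of both rates and dilution of the contrast. Nor is a planned test weakened, since SAP 4.3 and 4.4 provide only descriptive summaries and no between-arm test of adverse events is specified. The effect is confined to the laboratory part of one secondary safety endpoint.

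**What to change.** - Protocol 8.2: name the analytes in the discharge blood test.
- Protocol 6.6 and the CRF: record the latest available routine pre-ESD value of each analyte, with its date.
- Protocol 5.2.2 and SAP 4.1: count a laboratory early event only if its CTCAE grade is worse than that pre-ESD value. Report patients with no pre-ESD value separately.

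Reporting change from the pre-ESD value by arm is optional. The cost is transcribing values already in the chart and a few sentences of text; no extra sample is required and no treatment changes. The downside is that some patients will have no baseline value, and for them the question of new or old stays open.

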6.1. Study design

We aim to conduct an multicentric, open label, prospective randomized (1 :1) academic study comparing the submucosal injection using ORISE™ gel and glycerol in a specific population with superficial GI (pre)neoplastic lesions (see Schedule of assessments in Table 1). Patients will be referred by their gastroenterologist after index gastroscopy/colonoscopy showing a potential superficial (pre)neoplastic lesion.

6.2. Sample size and randomization

Based on available data of the dissection speed from Erasme, we calculated the dissection speed using the Orise gel and glycerol. These means and standard deviations are shown in the table below.

EndoscoPic Submucosal Dissection using gel versus glycerol for submucosal injection: a randomized controlled multicentric trial (EPSILON)

Version 1 – dated 21/07/2021

	Group Glyceol		Group Gel ORISE		Delta Speed (Gel - Glyceol)	
center	n	Speed (mm ² /min)	n	Speed (mm ² /min)	Speed (mm ² /min)	% of increase
Erasme	31	17.11 ± 18.27	10	22.24 ± 10.26	5.13 ± 4.61	23.06 %

A power analysis was performed using the results above to calculate the sample size. Using a two-sided Welch T-Test (groups with unequal variances) with an $\alpha = 0.05$ and power of 80%, with 1:1 randomization, 133 patients would be required to show a statistically significant difference between the groups. If this hypothesized difference is proven this would be a 23% increase in the speed of dissection. The results will also be stratified by site to see if any differences are observed, this will be performed using a generalized linear model.

A computer-based block randomization scheme will be created using block randomization and stratifying by center and by organ type (stomach/rectum). Data will be collected through a printed CRFs and then anonymized and entered into a central web based secured platform.

6.4. Study duration

Enrolment will begin Q2 2021 until Q2 2024, taking in account a follow-up of 3 weeks for each patient in order to evaluate the possible late adverse events.

6.5. Study periods

The study will comprise 3 periods:

- Day -15 to Day -1: The screening period will precede the randomized procedure.
- Day 0-1 : Treatment (ESD) Period (randomization and treatment)
- Week 1 to Week 2-4: follow-up.

EndoscoPic Submucosal Dissection using gel versus glycerol for submucosal injection: a randomized controlled multicentric trial (EPSILON)

Version 1 – dated 21/07/2021

6.6. Screening period (Day -15 to day -1)

The following screening procedures will be performed for all potential patients at the screening conducted during the screening period and prior to randomization:

- If possible, High-definition gastroscopy/rectoscopy for lesion evaluation (using chromoendoscopy and near-focus)
- Signature of informed consent witnessed by the Investigator or designated person.
- Patient randomization number allocation.
- Check medical history/demographics.
- Check inclusion/exclusion criteria
- Physical examination
- Check concomitant/prior medication (within 1 month prior to Screening)

6.7. Treatment period (Day 0-1)

- Procedure (Day 0): photo documentation of the lesion, ESD procedure, photo documentation of the specimen and resection field.
- Day 0 to +1 : clinical and biological follow-up and discharge (i.e. if no adverse effect is observed). Duration of hospital stay for subjects post procedure is determined by local healthcare practice and healthcare system guidelines and is left at the investigator's discretion.

6.8. Follow-up

- Clinical follow-up will be performed at Week 2-4 during outpatient visit or by phone call ; check AEs and occurrence of any clinical outcome

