- ESD is performed using a 25 G needle, a dual-knife-J with glycerol (standard solution) or ORISE™ gel in order to remove the lesion en-bloc. Additional saline injection through the electrosurgical knife will be left at the discretion of the endoscopist
- A follow-up visit is scheduled at 2-4 weeks

Study visits:

- Screening and baseline
- ESD procedure
- Post-treatment follow-up at 2_4 weeks

Number of patients (planned and analyzed): 133 patients by arm with a total of 266

Endpoints :**- Primary:**

- Increase the dissection speed of the ESD procedure (defined as the dissected surface (mm²)/ESD duration (min). The dissected surface is defined as maximal diameter of specimen (mm) x perpendicular minimal diameter of specimen (mm) measured on ex-vivo pinned stretched specimen onto a cork. ESD duration is defined as the time from first submucosal injection to final cut time.

- Secondary:

- Total procedure duration (from scope insertion to scope retrieval) (min)
- Number of per-procedural bleeding (+ severity scale: oozing / severe non pulsating/ severe pulsating)
- total hemostatic time (addition of each hemostasis time for each per-procedural bleeding)
- Need for haemostatic forceps during ESD
- Difficulty of the dissection (scale)
- Amount of submucosal solution (glycerol or gel) used for ESD in ml
- Combined use of saline through the knife during ESD (number and ml)
- Number of needle injection dots during ESD (initially / during ESD)
- Need to adjust electrosurgical settings during ESD
- Clear visualisation of the plane of dissection during ESD (scale) (defined in the protocole)
- Rate of en-bloc dissection (defined as endoscopic resection of the targeted area in one bloc)
- Rate of complete endoscopic resection (defined as endoscopic evaluation of complete removal of the targeted area in the treated organ)
- Quality assessment of the pathological specimen (absolute measure of the depth of resected submucosa on the specimen, rate of clear (horizontal and vertical) margins)

EndoscoPic Submucosal Dissection using gel versus glycerol for submucosal injection: a randomized controlled multicentric trial (EPSILON)

Version 1 – dated 21/07/2021

- Adverse events:
 - Per-procedural (incidence of all adverse technical events during the procedure)
 - Early (clinical and laboratory at 24 h post procedure according to CTCAE v 5.0)
 - Late (clinical at 3 weeks follow-up)

Main criteria for inclusion and exclusion:

- Inclusion:

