8.2. ESD procedure

First, the lesion will be closely inspected by high-resolution endoscopy with white light and narrow banding imaging (NBI) with near focus (GIF-HQ190 Olympus Medical System, Tokyo, Japan). Size, shape (Paris classification, LST classification for rectum), endoscopic features (NICE and JNET classification) and location will be reported¹¹⁻¹³.

The ESD procedures will be performed under general anesthesia with orotracheal intubation or under sedation following center experience. Carbon dioxide will be used for insufflation.

Using an HQ 190 Olympus gastroscope (EXERA III) or 290 series (LUCERA) in Japan or 1500EZ using Evis X1), fitted with a transparent cap at its end (D-206 or equivalent; Olympus), the gastric lesions will be delimited and marked by the ESD knife tip (i.e Dual-(J) Knife (Olympus Medical Systems, Tokyo, Japan), with soft coagulation mode (VIO 300 Effect 5, 50 watts; VIO3 E 5.5). Marking dots are not required for rectal lesions due to their clear delineation from the normal mucosa.

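### Patients could be kept unaware of which lifting solution was used, but the open-label design makes no provision for it, so patient-reported safety complaints are open to reporting bias (minor)

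*Protocol*

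**What the plan says.** Protocol 6.1 reads "We aim to conduct an multicentric, open label, prospective randomized (1 :1) academic study". Neither that section, the synopses nor the SAP describes blinding of the patient, of the person who makes the follow-up contact, or of whoever assesses adverse events.

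On the patient's state when the solution is used, Protocol 8.2 says "The ESD procedures will be performed under general anesthesia with orotracheal intubation or under sedation following center experience". The synopsis, section 6.5 and Table 1 place randomisation on the day of the procedure.

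On the late contact, Protocol 6.8 says "Clinical follow-up will be performed at Week 2-4 during outpatient visit or by phone call", with the task to "check AEs and occurrence of any clinical outcome". It does not say who makes the contact, how the mode is chosen or what is asked. The synopses of both documents mention only a visit: "A follow-up visit is scheduled at 2-4 weeks".

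Early and late adverse events are secondary endpoints (Protocol 5.2.2, SAP 4.1). SAP 4.4 summarises post-procedure data descriptively, and SAP 5.1 reports event rates per patient. Neither mentions the mode of contact.

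**The concern.** The operator cannot realistically be blinded: one product is a premixed gel in syringes and the other is a solution dyed by hand (Protocol section 3). The patient's position is different, because the solution is chosen and injected while the patient is anaesthetised or sedated. An unqualified open-label design gives up patient blinding where it appears achievable at low cost.

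Mild complaints after discharge, and the clinical part of the 24-hour assessment, depend largely on what the patient chooses to report. A patient who knows that the newer product was used may report more, or fewer, symptoms than one who does not. A difference in complaint rates between arms could then reflect reporting and not the product. At stake is how the descriptive safety comparison is read.

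**Working it through.** **1. Figures in the plan.** The documents give no expected adverse event rate, so there is no plan figure to reproduce on this point. The only related figure is 133 patients per arm (Protocol 6.2, SAP 3.1.1), set for dissection speed. It reproduces: with a difference of 22.24 − 17.11 = 5.13 and SDs of 18.27 and 10.26, a two-sided Welch test at 0.05 has power 79.95% at 132 per arm and 80.25% at 133. It is used below only as the arm size.

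**2. Can the patient be kept unaware?**
- Allocation is on Day 0 (synopsis, 6.5, Table 1). Section 6.6 also lists allocation of a randomisation number during screening, so the text should make clear that the arm is not disclosed then.
- Use of the solution is under anaesthesia or sedation (8.2). Sedation varies by centre and does not guarantee unawareness.
- Afterwards, the acid suppression after gastric ESD, the blood test and the overnight stay in 8.2 are described without reference to arm. The follow-up in 6.8 is also the same for both arms.

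Nothing in these passages requires the patient to know the arm.

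**3. Which outcomes can patient knowledge reach?**
- Not dissection speed, which is computed from specimen diameters and a timed interval.
- Not the 24-hour laboratory findings, nor the operator-rated and pathology endpoints.
- Serious events such as readmission: less than mild symptoms.
- Clinical complaints at 24 hours and at the Week 2-4 contact: yes.

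**4. Possible size from patient knowledge (assumed inputs).** Let the true rate p be the same in both arms, and let knowledge of the arm change reporting in one arm by a fraction r. The false gap is p × r.

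| p | r = 10% | r = 30% |
|---|---|---|
| 10% | 1 point | 3 points |
| 20% | 2 points | 6 points |

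The sign depends on whether knowledge raises or lowers reporting. If patients do not learn their arm, r = 0 and the gap is zero.

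For scale, the standard error of a difference with 133 per arm is:
- 10% versus 11%: √[(0.10×0.90 + 0.11×0.89)/133] = 3.8 points;
- 20% versus 26%: √[(0.20×0.80 + 0.26×0.74)/133] = 5.1 points.

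The false gap is therefore between about 0.3 (1/3.8) and 1.2 (6/5.1) standard errors.

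**5. Does the visit-or-phone option add bias?** Assume a visit captures 90% of events and a phone call 70%. With phone share f in an arm, the observed rate is p × [0.9(1 − f) + 0.7f].
- Same mix in both arms (f = 0.5): p × 0.80 in each, gap **zero**.
- Phone share 30% versus 70%: p × (0.84 − 0.76) = 0.08p, that is 0.8 points at p = 10% and 1.6 points at p = 20%.

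The second case enters an imbalance by arm as an input. The documents give no evidence of one, and randomisation stratified by centre (Protocol 6.2) balances centre habits in expectation.

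**The case against.** The case on the other side has four parts, and most of it stands.

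- **Patient knowledge is not shown.** A reader might infer from the open-label wording that patients are told their arm. The documents do not say so, and the information sheet was not available for review. What stands against the plan is that neither document says the arm is withheld.
- **Contact mode.** A reader might infer that a team aware of the arm picks visit or phone patient by patient, and that this biases the comparison. Protocol 6.8 says neither who chooses nor on what basis, and an unfixed mode alone does not bias a randomised comparison. On its own, this part is a missing detail.
- **Importance.** A reader might take late adverse events to be the only outcome after discharge. Section 6.8 also asks about other clinical outcomes, and SAP 4.1 lists related serious events through 30 days. Post-procedure data are summarised descriptively, with no planned hypothesis test of adverse events. Collection is also partly structured: CTCAE v5.0 for early events, and dates, seriousness and causality on the CRF (Protocol 10.1).
- **Limits of patient blinding.** It would not bring the bias to zero. Under Protocol 10.3 the sponsor and investigators judge the causality of serious events, with no blinded review described, and the products are billed locally (synopsis), so a bill could disclose the arm.

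These points limit the size and importance of the concern. They do not remove it: the patient's unawareness is available at low cost, and the plan does not use it.

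**Conclusion.** The point holds as a minor one. Patients could be kept unaware of the solution until the late contact, and the plan makes no provision for it. Patient-reported complaints at 24 hours and at Week 2-4 may therefore be influenced by knowledge of the arm.

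The size is unknown. The 1 to 6 points rest on an assumed true rate of 10-20% and an assumed 10-30% change in reporting in one arm, and they apply only if patients learn their arm. The exposure is confined to descriptive, subjective secondary safety outcomes. The documents do not support the stronger conclusion that the safety comparison is biased as designed, or that the choice between visit and phone is itself a source of bias.

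**What to change.** In Protocol 6.1 and 6.8, and in the SAP where it applies:

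1. State that patients are not told which solution was used until their Week 2-4 contact is complete, and describe the design as patient-blinded with an open-label operator. Say the same in the information sheet.
2. Use the same written adverse event question list in both arms.
3. Have each centre set one default contact mode, record the mode actually used on the CRF, and tabulate it by arm.
4. Reconcile the visit in both synopses with the visit or phone call in 6.8. The same edit can reconcile the late adverse event time point, given as 3 weeks in the synopses, 2-3 weeks in Protocol 5.2.2 and SAP 4.1, and Week 2-4 in 6.8.

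**Cost:** wording in the protocol, SAP and information sheet, a CRF field and one table; no extra visits. **Downside:** discharge papers, records that patients can access and bills may reveal the arm to some patients, and the staff who elicit and judge events remain unblinded. Bias is reduced, not removed.
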